**Listing 16.2.6.1.1**  
**Local TETRAS Performance Subscale and Upper Limb Subscale Scores**  
**All Subjects**

Subject ID	Protocol Amendment	Study Visit	CAD-1883 Administered In-Clinic?	Was Assessment Completed?	Date/Time of Assessment (Study Day)	Number of Minutes Assessment Started after Dosing	Was the Videography Uploaded to Portal?	Item	Result
XXXXXX	X.X	XXXXXX	XXX	Yes	DDMMYYYY/HH:MM (X)	XX	Yes	Head Tremor	XX
								Face (including jaw) Tremor	XX
								Voice tremor	XX
								Upper limb tremor: Forward outstretched postural tremor – Right	XX
								...	
								TETRAS-PS	XX
								Upper Limb Subscale Score	
								TETRAS-PS	XX
								Upper Limb Tremor (Item 4) Score	
								TETRAS-PS	XX
								Total Score	

Abbreviation: TETRAS-PS = Tremor Research Group Essential Tremor Rating Assessment Scale Performance Subscale.

Note: Study day is calculated relative to the date of first dose of study drug. For pre-dose: study day= Assessment Date – Date of the first dose of date; For post-dose: study day= Assessment Date – first dose date + 1.

Each individual item question score ranges from 0 to 4, where higher scores indicate worse quality of life.

TETRAS-PS Total score is derived as the sum of the 16 individual item scores (only the maximum of the item 5, lower limb tremor scores will be counted), with a maximum total score of 64.

TETRAS-PS Upper Limb Subscale score is derived as the sum of the item 4, item 6, item 7 and item 8 scores (forward outstretched postural tremor, lateral “wing beating” postural tremor, kinetic tremor, Archimedes spirals, and dot approximation task from both sides of the body, as well as handwriting, with a maximum total score of 44.

TETRAS-PS Upper Limb Tremor (Item 4) Total score is derived as the sum of the 6 item 4 scores (forward outstretched postural tremor, lateral “wing beating” postural tremor, and kinetic tremor scores) from both sides of the body, with a maximum total score of 24.

**Programming Note:** If Assessment was not completed or videography was not uploaded to the portal, concatenate reason. CAD-1883 Administered In-Clinic will come from EX CRF, if date of in-clinic administration at the corresponding visit is not null. If not administered in clinic, concatenate reason not administered with a semicolon.

**Listing 16.2.6.1.2**  
Central TETRAS Performance Subscale and Upper Limb Subscale Scores  
All Subjects

**Same Shell as Listing 16.2.6.1.1**

Commercially Confidential Information

Commercially Confidential Information

Commercially Confidential Information

Commercially Confidential Information

Listing 16.2.6.6  
Wearable Sensor (Kinesia) Scores  
All Subjects

Subject ID	Protocol Amendment	Study Visit	Date/Time of Assessment (Study Day)	Side	Task	Kinesia Score	Tremor Amplitude	Tremor Frequency	Finger-Chin-Finger Quality
XXXXXX	X.X	XXXXXX	DDMMYYYY/HH:MM (X)	Left	Extended arms posture	X	XX	XX	XXXX
					Wing-beating posture	X	XX	XX	XXXX
					Kinetic "finger-to-chin" movement	X	XX	XX	XXXX
				Right	Arm on table posture	X	XX	XX	XXXX
					Extended arms posture	X	XX	XX	XXXX
					Wing-beating posture	X	XX	XX	XXXX
				Both	Kinetic "finger-to-chin" movement	X	XX	XX	XXXX
					Arm on table posture	X	XX	XX	XXXX
					Kinesia Upper Limb Tremor Score	X	XX	XX	XXXX

Note: Study day is calculated relative to the date of first dose of study drug.

Kinesia score ranges from 0 to 4; higher scores indicate more severe tremor. Finger-Chin-Finger quality values of 1 represent good quality and values of 0 represent poor quality. Kinesia Upper Limb Tremor score is derived as the sum of the scores from the extended arms posture, wing-beating posture, and kinetic "finger-to-chin" wearable sensor maneuvers from both sides of the body, with a maximum total score of 24.

**Programming Note:** If assessment was done at home, place 'NA' in study visit column and add to abbreviations.

Listing 16.2.7  
Adverse Events  
All Subjects

Subject ID	Protocol Amendment	TEAE/Disc	System Organ Class/ Preferred Term/ Verbatim Term	Start Date/Time (Study Day)/ End Date/Time (Study Day)	Severity/ Relationship	Action Taken/ Outcome	Serious (SAE)?/ Criteria Met
XXXXXX	X.X	Yes/No	XXXXXXXXXXXXXXXXXXXX/ XXXXXXXXXXXXXXXXXXXX XXXXXXXXXXXXXXXXXXXX	DDMMYYYY/HH:MM (X)/ DDMMYYYY/HH:MM (X)	XXXXXXXXXX/ XXXXXXXXXX	XXXXXXXXXX/ XXXXXXXXXX	Yes/xxxxxx
XXXXXX	X.X	No/No	XXXXXXXXXXXXXXXXXXXX/ XXXXXXXXXXXXXXXXXXXX XXXXXXXXXXXXXXXXXXXX	DDMMYYYY/HH:MM (X)/ DDMMYYYY/HH:MM (X)	XXXXXXXXXX/ XXXXXXXXXX	XXXXXXXXXX/ XXXXXXXXXX	No
		Yes/Yes	XXXXXXXXXXXXXXXXXXXX/ XXXXXXXXXXXXXXXXXXXX XXXXXXXXXXXXXXXXXXXXXX	DDMMYYYY/HH:MM (X))/ DDMMYYYY/HH:MM (X)	XXXXXXXXXX/ XXXXXXXXXX	XXXXXXXXXX/ XXXXXXXXXX	

DISC = Discontinued, SAE = Serious Adverse Event, TEAE = Treatment Emergent Adverse Event

Note: Study day is calculated relative to the date of first dose of study drug. For pre-dose: study day= Start/End Date – Date of the first dose of date; For post-dose: study day= Start/End Date – first dose date + 1.

**Programming note:** If time missing, display “- - -”. If Serious? is Yes, concatenate all serious criteria marked as Yes with a semicolon. If no events meet the criteria for display, present “No events are reported.” SOC & PT text should be in proper case in table, as shown in the shell. “Other Action Taken” will be either None, Medication Required, Relevant Procedure, or Other; if specify text is needed, concatenate “Relevant Procedure.” or “Other:” with the text.

Listing 16.2.8.1.1  
Clinical Laboratory Data: Hematology  
All Subjects

Subject ID: XXXXXX, Protocol Amendment: X.X, Sex: M/F, Age: XX, Date of First/Last Dose (Study Day): DDMMYYYY (X)/ DDMMYYYY (X)

Parameter (unit)	Study Visit	Date/Time of Assessment (Study Day)	Standard Results	Change from Baseline (%) [1]	Reference Range [2]	Reference Range Flag	Lab Panel	Comments/Reason Not Done
Hemoglobin (unit)	XXXXXX	DDMMYYYY/HH:MM (X)	XX		XX – YY		XXXXXXX	
	XXXXXX	DDMMYYYY/HH:MM (X)	XX	XX (XX.X)	XX – YY		XXXXXXX	
	XXXXXX	DDMMYYYY/HH:MM (X)	XX		XX – YY		XXXXXXX	
	XXXXXX	DDMMYYYY/HH:MM (X)	XX		XX – YY	XXX	XXXXXXX	
	XXXXXX	DDMMYYYY/HH:MM (X)	XX		XX – YY		XXXXXXX	
	XXXXXX	DDMMYYYY/HH:MM (X)	XX		XX – YY		XXXXXXX	
	XXXXXX	DDMMYYYY/HH:MM (X)	XX		XX – YY		XXXXXXX	
	XXXXXX	DDMMYYYY/HH:MM (X)	XX		XX – YY		XXXXXXX	
	XXXXXX	DDMMYYYY/HH:MM (X)	ND					XXXXXXX

Abbreviations: AL = abnormal-low; AH = abnormal-high; CS = clinically significant; NCS = not clinically significant; ND = not done.

Note: Study day is calculated relative to the date of first dose of study drug. For pre-dose: study day= Assessment Date – Date of the first dose of date; For post-dose: study day= Assessment Date – first dose date + 1.

[1] Baseline is the last observation recorded prior to the first dose of treatment.

[2] Reference range is used to identify potentially clinically significant laboratory values.

**Programming note:** Update abbreviations to reflect actual data. If test was not done, set results to ND; make sure last column is populated accordingly. Do not display serum HCG results in this listing. For reference range flag, concatenate AL or AH with clinical significance like "XX-YY" (eg, AL-CS). Sort by Subject ID, Treatment, Sex, Age, First Dose Date, Parameter, Study visit, Date of Assessment.

Listing 16.2.8.1.2  
Clinical Laboratory Data: Serum Chemistry  
All Subjects

**Same shell as Listing 16.2.8.1.1**

Listing 16.2.8.1.3  
Clinical Laboratory Data: Urinalysis  
All Subjects

**Same shell as Listing 16.2.8.1.1**

Listing 16.2.8.1.4  
Clinical Laboratory Data: Biomarker Panel for Renal Tubular Injury  
All Subjects

Subject ID: XXXXXX, Protocol Amendment: X.X, Sex: M/F, Age: XX, Date of First/Last Dose (Study Day): DDMMYY (X)/ DDMMYY (X)

Study Visit	Physical Exam Performed?	Any CS Changes since Last Visit?	Exam Date (Study Day)	Body System	Result	Abnormal Findings	Clinically Significant?
XXXXXX	Yes	NA	DDMMYY (XX) DDMMYY (XX)	XXXXXX XXXXXX	NORMAL NORMAL		
XXXXXX	Yes	XX	DDMMYY (XX)	XXXXXX	ABNORMAL	XXXXXXXXXXXX	No
XXXXXX	No; XXXXX		DDMMYY (XX)	XXXXXX	NORMAL		

Abbreviations: CS = clinically significant; NA = not applicable.

Note: Study day is calculated relative to the date of first dose of study drug. For pre-dose: study day= Exam Date – Date of the first dose of date; For post-dose: study day= Exam Date – first dose date + 1.

**Programming Note:** If exam was not performed, concatenate reason. Any Clinically Significant Changes since Last Visit? will be NA at the Screening visit.

Listing 16.2.8.2.2  
Neurological Examination  
All Subjects

Subject ID: XXXXXX, Protocol Amendment: X.X, Sex: M/F, Age: XX, Date of First/Last Dose (Study Day): DDMMYYYY (X) / DDMMYYYY (X)

Study Visit	Neurological Examination Performed?	Any Clinically Significant Changes since Last Visit?	Exam Date (Study Day)	Body System	Result	Abnormal Findings	Clinically Significant?
XXXXXX	Yes	XX	DDMMYYYY (XX)	XXXXXX	NORMAL		
XXXXXX	Yes	XX	DDMMYYYY (XX)	XXXXXX	ABNORMAL	XXXXXXXXXXXX	No
XXXXXX	No	XX	DDMMYYYY (XX)	XXXXXX	NORMAL		

Abbreviations: CS = clinically significant; NA = not applicable.

Note: Study day is calculated relative to the date of first dose of study drug. For pre-dose: study day= Exam Date – Date of the first dose of date; For post-dose: study day= Exam Date – first dose date + 1.

**Programming Note:** If exam was not performed, concatenate reason. Any Clinically Significant Changes since Last Visit? will be NA at the Screening visit.

Listing 16.2.8.3.1  
Vital Signs  
All Subjects

Subject ID	Protocol Amendment	Study Visit	Were Vital Signs Collected?	Date/Time Collected (Study Day)	Body Temperature (F)	Respiration Rate (breaths/min)	Height (cm)	Weight (kg)	Abnormal?
XXXXXX	X.X	XXXXXX	XXX	DDMMYYYY/ HH:MM (X)	XX.X	XX	XX.X	XX.X	XXX
				DDMMYYYY/ HH:MM (X)	XX.X	XX		XXX	Commercially Confidential Information
XXXXXX	X.X	XXXXXX	XXX; XXXXXX	DDMMYYYY/ HH:MM (X)	XX.X	XX		XXX	
				DDMMYYYY/ HH:MM (X)	ND	ND		ND	

Abbreviation: CCI ND = not done.

Note: Study day is calculated relative to the date of first dose of study drug. For pre-dose: study day= Assessment Date – Date of the first dose of date; For post-dose: study day= Assessment Date – first dose date + 1.

Abnormal vital signs are as follows: CCI Systolic blood pressure >140 mmHg; Systolic blood pressure <90 mmHg; Diastolic blood pressure >90 mmHg; Diastolic blood pressure <60 mmHg; Heart rate >100 bpm; Heart rate <50 bpm; Respiration rate >20 breaths/min; Respiration rate <12 breaths/min; Oral temperature >99.5 °F; Oral temperature <97 °F.

[1] Treatment is based on treatment received.

**Programming Note:** If vital signs were not collected, concatenate reason, as shown above. If a measurement is outside the normal range, place an asterisk (\*) next to the value in the cell.

**Listing 16.2.8.3.2**  
**Blood Pressure and Orthostatic Vital Signs**  
**All Subjects**

Subject ID	Protocol Amendment	Study Visit/ Date/Time Collected (Study Day)	Measurement No. / Total No. Measurements	Position	Parameter (unit)	Result	Change from Baseline	Orthostatic Hypotension? [1]
XXXXXX	1  2 or 3	XXXXXX/ DDMMYYYY/ HH:MM (X)	X / X	Standing	SBP (mmHg)	XXX	XXX	NA
		XXXXXX/ DDMMYYYY/ HH:MM (X)	X / X	Standing	DBP (mmHg)	XXX	XXX	XX
		XXXXXX/ DDMMYYYY/ HH:MM (X)	X / X	Standing	HR (bpm)	XXX	XXX	XX
		XXXXXX/ DDMMYYYY/ HH:MM (X)	NA	Supine	SBP (mmHg)	ND	NA	NA
		XXXXXX/ DDMMYYYY/ HH:MM (X)	X / X	Supine	DBP (mmHg)	XXX	XXX	XX
		XXXXXX/ DDMMYYYY/ HH:MM (X)	X / X	Supine	HR (bpm)	XXX	XXX	XX
		XXXXXX/ DDMMYYYY/ HH:MM (X)	X / X	Standing-Average	SBP (mmHg)	XXX	XXX	NA
		XXXXXX/ DDMMYYYY/ HH:MM (X)	X / X	Average	DBP (mmHg)	XXX	XXX	XX
		XXXXXX/ DDMMYYYY/ HH:MM (X)	X / X	Average	HR (bpm)	XXX	XXX	XX
		XXXXXX/ HH:MM (X)						

Note: Study day is calculated relative to the date of first dose of study drug. For pre-dose: study day= Assessment Date – Date of the first dose of date; For post-dose: study day= Assessment Date – first dose date + 1.

[1] Orthostatic hypotension is defined as a reduction in SBP of 20 mmHg or more, and/or a reduction in DBP of 10 mmHg or more, for the standing measurement compared to the supine or semi-supine measurement.

**Programming Note:** If measurements are not orthostatic, put 'NA' in the "Measurement Number/Was Measurement Performed?" and "Average" Columns. If a measurement is outside the normal range, place an asterisk (\*) next to the value in the cell.

Please use "Standing-Average", "Supine-Average" respectively for averaged values. "Standing-Supine" for difference.

**Listing 16.2.8.4.1**  
**Qualitative 12-Lead Electrocardiogram (ECG) Investigator Results**  
**All Subjects**

Subject ID	Protocol Amendment	3 ECGs Performed Per Protocol?	Time Point	Study Visit/ Date of Assessment (Study Day)	Time			Reason not Performed	Investigator Interpretation	Comments	
					1 st Reading	2 nd Reading	3 rd Reading				
XXXXXX	X.X	Yes	XX	XXXXX / DDMMYYYY (XX)	HH:MM	HH:MM	HH:MM		Normal	XXXXXXXXXXXXXX	
				XXXXX / DDMMYYYY (XX)	HH:MM	HH:MM	HH:MM				
				XXXXX / DDMMYYYY (XX)	HH:MM	HH:MM	HH:MM		Abnormal-NCS		
				XXXXX / DDMMYYYY (XX)	HH:MM	HH:MM	HH:MM				
				XXXXX / DDMMYYYY (XX)	HH:MM	HH:MM	HH:MM		Normal		
				XXXXX / DDMMYYYY (XX)							
XXXXXX	X.X	No	XX						XXXXXXXXXXXX		

Abbreviations: CS = clinically significant; NCS = not clinically significant.

Note: Study day is calculated relative to the date of first dose of study drug. For pre-dose: study day= Assessment Date – Date of the first dose of date; For post-dose: study day= Assessment Date – first dose date + 1.

***Programming Note:*** time point will be pre-dose or post-dose.

**Listing 16.2.8.4.2**  
**12-Lead Electrocardiogram (ECG) Central Results**  
**All Subjects**

Subject ID	Protocol Amendment	Study Visit	Date/Time of ECG (Study Day)	Overall Interpretation	PR Interval (msec)	QRS Interval (msec)	QT Interval (msec)	QTcF Interval (msec)
XXXXXX	1	XXXXX	DDMMYYYY/ HH:MM (XX)	XXXXXXXX	XXX	XXX	XXX	XXX
		XXXXX	DDMMYYYY/ HH:MM (XX)	XXXXXXXXXXXX	XXX	XXX	XXX	XXX
		XXXXX	DDMMYYYY/ HH:MM (XX) ND	XXXXXXXXXX	XXX	XXX	XXX	XXX
XXXXXX	2 or 3	XXXXX	DDMMYYYY/ HH:MM (XX)	XXXXXXXX;XXXXX	XXX	XXX	XXX	XXX
		XXXXX	DDMMYYYY/ HH:MM (XX)	XXXXXXXXXXXX	XXXX	XXXX	XXXX	XXXX

ECG = electrocardiogram; ND = not done.

Note: Study day is calculated relative to the date of first dose of study drug. For pre-dose: study day= ECG Date – Date of the first dose of date; For post-dose: study day= ECG Date – first dose date + 1.

**Programming Note:** If a measurement is outside the normal range, place an asterisk (\*) next to the value in the cell.

Commercially Confidential Information

Commercially Confidential Information

**Listing 16.2.8.6**  
**Columbia-Suicide Severity Rating Scale (C-SSRS)**  
**All Subjects**

Subject ID	Protocol Version	Study Visit	Date of Assessment (Study Day)	Reference Period	Reason not Completed	Category	Assessment	Result
XXXXXX	X.X	XXXXXX	DDMMYYYY (XX)	Baseline/ Screening		Suicidal Ideation	1. Wish to be dead  If yes, describe: 2. Non-Specific Active Suicidal Thoughts  If yes, describe: 3. Active Suicidal Ideation with Any Methods (not Plan) without Intent to Act  If yes, describe: 4. Active Suicidal Ideation with Some Intent to Act, without Specific Plan  If yes, describe: 5. Active Suicidal Ideation with Specific Plan and Intent  If yes, describe: Most Severe Ideation Type # (1-5) Description of Ideation	XX  XX  XX  XX  XX  X XXXXXXXXXXXX XXXX 1 = 1-4 hours/a lot of time 1 = Fleeting – few seconds or minutes 1 = Easily able to control thoughts
						Intensity of Ideation	Frequency	
							Duration	
							Controllability	
						...	...	...

[figure not shown]
Note: All subjects received CAD-1883 300 mg BID. At the Pre-dose visit, the “baseline” version of the C-SSRS was administered. This version assesses Suicidal Ideation and Suicidal Behavior during the subject’s lifetime and during a predefined period. At the Day 21 visit (and the Early Termination visit for subjects withdrawing early), the “since last visit” version was administered.

Study day is calculated relative to the date of the first dose of study drug.

#### **14.4. Planned Figure Shells**

Commercially Confidential Information

Figure 14.2.1.1.4  
Central and Local TETRAS-PS Total Scores by Study Visit  
Full Analysis Set

Abbreviation: TETRAS-PS = Tremor Research Group Essential Tremor Rating Assessment Scale (TETRAS)-performance subscale (PS).

Note: TETRAS-PS Total score is derived as the sum of all of the individual item scores. Each individual item question score ranges from 0 to 4, where higher scores indicate worse quality of life. Pearson correlation coefficient and regression lines are presented for all study visits.

Reference Table: 14.2.1.1.4

SOURCE: Listings 16.2.6.1.1, 16.2.6.1.2

**Programming Note:** Check Section 8.3.2 of SAP. If Spearman correlation coefficient is used, update footnote [1] accordingly. A separate graph will be produced for each study visit.

Commercially Confidential Information

Figure 14.2.1.2.3  
Central and Local TETRAS-PS Upper Limb Subscale Scores by Study Visit  
Full Analysis Set

**Same shell as Figure 14.2.1.1.4**

Y-axis: Central Score  
X-axis: Local Score

Programming notes: A separate graph will be produced for each study visit. Update footnote to read: TETRAS-PS Upper Limb Subscale score is derived as the sum of the item 4, item 6, item 7 and item 8 scores (forward outstretched postural tremor, lateral “wing beating” postural tremor, kinetic tremor, Archimedes spirals, and dot approximation task from both sides of the body, as well as handwriting, with a maximum total score of 44.

Reference Table: 14.2.1.2.3

SOURCE: Listings 16.2.6.1.1, 16.2.6.1.2

Commercially Confidential Information

Figure 14.2.1.3.2  
Central and Local TETRAS-PS Upper Limb Tremor (Item 4) Scores by Study Visit  
Full Analysis Set

**Same shell as Figure 14.2.1.1.4**

Y-axis: Central Score

X-axis: Local Score

Programming notes: A separate graph will be produced for each study visit. Update footnote to read: TETRAS-PS Upper Limb Tremor (Item 4) Total score is derived as the sum of the 6 item 4 scores (forward outstretched postural tremor, lateral “wing beating” postural tremor, and kinetic tremor scores) from both sides of the body, with a maximum total score of 24.

Reference Table: 14.2.1.3.2

SOURCE: Listings 16.2.6.1.1 and, 16.2.6.1.2

Commercially Confidential Information

Commercially Confidential Information

Figure 14.2.4  
TETRAS-PS and Wearable Sensor (Kinesia) Upper Limb Tremor Scores by Study Visit  
Full Analysis Set

**Same shell as Figure 14.2.1.1.4**

Y-axis: Central Score  
X-axis: Local Score

Programming notes: A separate graph will be produced for each study visit. Update the footnote to read: TETRAS-PS Upper Limb Tremor (Item 4) Total score is derived as the sum of the 6 item 4 scores (forward outstretched postural tremor, lateral “wing beating” postural tremor, and kinetic tremor scores) from both sides of the body, with a maximum total score of 24. Kinesia Upper Limb Tremor score is derived as the sum of the scores from the extended arms posture, wing-beating posture, and kinetic “finger-to-chin” wearable sensor maneuvers from both sides of the body, with a maximum total score of 24.

[figure not shown]
Reference Table: 14.2.6.1

SOURCE: Listings 16.2.6.1.1 and 16.2.6.6.1

Commercially Confidential Information

Commercially Confidential Information

Figure 14.5  
Geometric Mean (GM) Composite Measure (CM) of Kidney Injury Biomarkers by Study Visit  
Safety Population

Programming note: Remove "GM CM of CAD1883-201 subjects as of Fri, 5/17/2019" from the graph. The threshold values need to be updated per the user guide (Threshold=1.18 with n=20).

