### **11.2.4 Sample Size Determination**

Approximately 30 subjects will be enrolled. No formal statistical power analysis was conducted. Each subject will be assessed for change from their own Baseline.

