#### **3.2. Sample Size and Power**

Up to 30 subjects will be enrolled. No formal statistical power analysis was conducted.

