#### 6.1.2. Categorization of Subjects

All subjects will be categorized into the following 2 groups based on under which protocol amendment they were enrolled:

- Cohort-1: Subjects enrolled under Protocol Amendment 1.0
- Cohort-2: Subjects enrolled under Protocol Amendment 2.0 or 3.0

All analyses will be presented overall and by cohort.

Commercially Confidential Information

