## **9.7 Kidney safety Composite Measure Biomarker**

The following 6 kidney safety composite measure biomarkers were tested using urine sample: uCreatine (uCr), uClusterin (uCLU) , uCystatin-C (uCysC), uKidney Injury Molecule-1 (uKIM-1), u N-Acetyl-beta-D-Glucosaminidase (uNAG), Neutrophil Gelatinase-Associated Lipocalin (uNGAL) and uOsteopontin (uOPN). Measured concentration is first normalized by dividing it by the concentration of uCR at the same timepoint. The fold change from baseline at a given timepoint is then calculated using the normalized concentration at a time point divided by the normalized concentration at baseline. For example, the normalized uCysC concentration at a given timepoint is calculated as the concentration of CysC at that timepoint divided by the concentration of uCr at the same timepoint. The uCysC fold change from baseline at a given timepoint is calculated as the normalized CysC concentration at a given timepoint divided by the normalized uCysC concentration at baseline. Similar calculations apply to other composite measures.

Commercially Confidential Information

Commercially Confidential Information

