## Figure 2: Planned Table Shells

Table 14.1.1  
Subject Disposition  
All Enrolled Subjects

Category	Cohort-1 (N=XX)	Cohort-2 (N=XX)	Overall (N=XX)
Enrolled	XX	XX	XX
Analysis Populations:			
Safety Population [1]	XX (XX.X%)	XX (XX.X%)	XX (XX.X%)
FAS Population [2]	XX (XX.X%)	XX (XX.X%)	XX (XX.X%)
Commercially Confidential Information	XX (XX.X%)	XX (XX.X%)	XX (XX.X%)
Per-Protocol Population [4]	XX (XX.X%)	XX (XX.X%)	XX (XX.X%)
Completed Study	XX (XX.X%)	XX (XX.X%)	XX (XX.X%)
Prematurely Discontinued from Study	XX (XX.X%)	XX (XX.X%)	XX (XX.X%)
Reason for Discontinuation:			
Adverse Event	XX (XX.X%)	XX (XX.X%)	XX (XX.X%)
Death	XX (XX.X%)	XX (XX.X%)	XX (XX.X%)
Lack of Efficacy	XX (XX.X%)	XX (XX.X%)	XX (XX.X%)
Lost to Follow-Up	XX (XX.X%)	XX (XX.X%)	XX (XX.X%)
Newly Emerged Exclusion Criteria During Study	XX (XX.X%)	XX (XX.X%)	XX (XX.X%)
Non-Compliance with Study Drug	XX (XX.X%)	XX (XX.X%)	XX (XX.X%)
Physician Decision	XX (XX.X%)	XX (XX.X%)	XX (XX.X%)
Pregnancy	XX (XX.X%)	XX (XX.X%)	XX (XX.X%)
Protocol Violation	XX (XX.X%)	XX (XX.X%)	XX (XX.X%)
Study Terminated by Sponsor	XX (XX.X%)	XX (XX.X%)	XX (XX.X%)
Withdrawal by Subject	XX (XX.X%)	XX (XX.X%)	XX (XX.X%)
Other	XX (XX.X%)	XX (XX.X%)	XX (XX.X%)

Abbreviations: ADL = activities of daily living; FAS = full analysis set; ICF = informed consent form; CCI ; PS = performance subscale; TETRAS = Tremor Research Group Essential Tremor Rating Assessment Scale.

Note: Cohort-1 is composed of subjects enrolled under the Protocol Amendment 1. Protocol Amendment 1 was finalized on 03 Dec 2018 with dosing interval of 8±2 hours during entire treatment period (Day 1-14). Cohort-2 is composed of subjects enrolled under Amendment 2 or 3. Amendment 2 was finalized on 09 May 2019 and Amendment 3 on 09 July 2019. Dosing interval was changed to 4-5 hours on Days 1, 7 and 14 in both Amendments 2 and 3.

Percentages are n/Number of subjects in the enrolled\*100.

[1] The Safety population includes all subjects who took at least 1 dose of study drug.

[2] The FAS consists of subjects in the Safety Population at least one TETRAS-PS assessment Total Score at Day 7, Day 14 or early termination visit. The FAS will be used to summarize all efficacy data.

[3] Commercially Confidential Information

[4] The Per-Protocol Population includes all subjects in the FAS who did not have any major protocol deviation and follow the study protocol for TETRAS-PS assessment.  
Personal Protected Data

Source: Listing 16.2.1.1

Table 14.1.2.1  

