**Programming note:**

Parameters are uCreatine (uCr), uClusterin (uCLU) , uCystatin-C (uCysC), uKidney Injury Molecule-1 (uKIM-1), u N-Acetyl-beta-D-Glucosaminidase (uNAG), Neutrophil Gelatinase-Associated Lipocalin (uNGAL) and uOsteopontin (uOPN).

Keep the decimal places as exactly the same as what is shown in this table shells

Exten the table for visits Day 7, 14 and 21.

Table 14.3.5.4.2

Geometric Mean (GM) Composite Measure (CM) on Quantitative Biomarker Panel for Renal Tubular Injury Results by Study Visit  
Safety Population

Visit	Number of Subjects (N=xx)	GM CM
Baseline	xx	x.xx
Day 1	xx	x.xx
Day 7	xx	x.xx
Day 14	xx	x.xx
Day 21	xx	x.xx

GM CM = Geometric Mean (GM) Composite Measure (CM)

***Programming note:*** Update footnote to SOURCE: Listing 16.2.8.1.4

Table 14.3.6.1.1  
Summary of Vital Signs by Study Visit  
Safety Population

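### The renal tubular injury composite is shown as one pooled geometric mean per visit against a threshold stated only for n=20, so a rise confined to a few subjects or to one cohort can stay below the line

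*SAP*

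**What the plan says.** SAP 9.7 introduces the panel: "The following 6 kidney safety composite measure biomarkers were tested using urine sample". Each marker is divided by urine creatinine from the same sample and then by its own baseline, which gives a fold change. The text after that definition is redacted.

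The composite appears in two planned outputs.

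- Table 14.3.5.4.2 (SAP 14.2), titled "Geometric Mean (GM) Composite Measure (CM) on Quantitative Biomarker Panel for Renal Tubular Injury Results by Study Visit", has one row per visit from Baseline to Day 21. Its only entries are the number of subjects and the GM CM.
- Figure 14.5 (SAP 14.4) plots the same quantity. The image is not reproduced, but its programming note says: "The threshold values need to be updated per the user guide (Threshold=1.18 with n=20".

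Three other statements bear on these outputs.

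- SAP 6.1.2: "All analyses will be presented overall and by cohort".
- Note to Table 14.1.1: "Dosing interval was changed to 4-5 hours on Days 1, 7 and 14 in both Amendments 2 and 3". Cohort-1 kept the interval of 8±2 hours throughout.
- SAP 3.2: "Up to 30 subjects will be enrolled". Protocol 11.2.4: "Approximately 30 subjects will be enrolled. No formal statistical power analysis was conducted".

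**The concern.** Safety is the primary objective, and this panel is a dedicated renal safety measure taken at Baseline and at all four later visits. Its headline summary has three weaknesses.

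1. It averages over everyone, so a rise in a minority is shrunk towards 1.0, and nothing beside the average shows spread or uncertainty.
2. It pools two cohorts that SAP 6.1.2 says must be shown separately. They were dosed at different intervals on Days 1, 7 and 14, which are exactly the on-drug days when the panel is sampled. Table 14.3.5.4.1, for the single markers, does have cohort columns.
3. The comparison line is quoted for 20 subjects, and the evaluable number may be anything up to 30 overall and smaller within a cohort.

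The risk is that a point below the line is taken as reassurance that the data at this sample size cannot give.

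**Working it through.** **Can 1.18 be reproduced?** No. The visible text gives no variance, percentile or formula for it, SAP 9.7 is partly redacted, and the cited user guide is not available. It is taken as given, for n=20.

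**Inputs**
- Threshold 1.18 at n=20 (Figure 14.5 programming note).
- Up to 30 subjects (SAP 3.2).
- Assumed: a subject's composite is the geometric mean of the six marker fold changes, and the GM CM is the geometric mean over subjects. The visible text does not give the formula.

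**Dilution.** If k of n subjects have an F-fold composite and the rest are at exactly 1.0, then GM CM = F^(k/n).

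**At n=20, where 1.18 applies as written**
- 5-fold in 2 of 20: 5^(2/20) = 1.175, below 1.18.
- 10-fold in 1 of 20: 10^(1/20) = 1.122, below.
- The largest rise in 2 of 20 that stays below is 1.18^(20/2) = 5.23-fold. The 5-fold case is therefore close to the limit; with 19 evaluable it gives 5^(2/19) = 1.185 and crosses. The 10-fold case in one subject has a clear margin.

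**At n=30.** The documents give no threshold. Assuming it shrinks as 1/sqrt(n) on the log scale:
- Threshold = exp(ln 1.18 × sqrt(20/30)) = 1.145.
- 3-fold in 3 of 30: 3^(3/30) = 1.116, below.
- 5-fold in 2 of 30: 5^(2/30) = 1.113, below.
- 10-fold in 1 of 30: 10^(1/30) = 1.080, below.
- Break-even for 3 of 30: 1.145^(30/3), which is 3.86-fold from the unrounded threshold.

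**With sampling noise.** Reading 1.18 at n=20 as a one-sided 5% limit (assumed) implies a between-subject log SD of ln 1.18 / 1.645 × sqrt(20) = 0.45. For a 3-fold rise in 3 of 30, the chance that the GM CM stays under 1.145 is Phi((ln 1.145 − 0.1 × ln 3) / (0.45/sqrt(30))) = 62%. It is 68% at an SD of 0.3 and 59% at 0.6.

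**One cohort affected.** With 15 per cohort (assumed) and the other cohort at 1.0, the pooled value is the square root of the affected cohort's value. That cohort can reach 1.145² = 1.31 before the pooled value crosses. Under the same scaling, its own threshold at n=15 would be exp(ln 1.18 × sqrt(20/15)) = 1.21. A cohort value between 1.21 and 1.31 would thus exceed its own line while the pooled point stayed below.

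**The case against.** The strongest reply is that the composite is not the only view of the kidney.

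- Table 14.3.5.4.1 gives each marker's fold change with mean, SD, median, minimum and maximum, by cohort and overall. On the assumed formula, a subject with a 5-fold composite must have at least one marker raised 5-fold or more, so a maximum would show it. If a single marker rose 5-fold in 3 of 30, the GM CM would be only 5^(3/180) = 1.027, but that table would show a maximum of at least 5 and, with the other 27 at 1.0, a mean of 1.40 (SD 1.22).
- The biomarker data are listed, and SAP 13.5 puts all calculated variables in the listings.
- Chemistry and urinalysis have shift tables, and clinically significant findings become adverse events.
- SAP 9.7 is redacted where the formula and any reading rule would be expected. The programming note also speaks of threshold values in the plural, so a value matched to n may already be intended.

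Most of this stands. A reader might infer that renal safety is decided by the line alone, and that a 5-fold rise in 3 of 30 would pass as no signal. The documents do not support that. No visible text makes the threshold the sole criterion. The value 1.18 belongs to n=20. The result 5^(3/30) = 1.1746 is under 1.18 by only 0.0054, turns into 1.1812 with 29 evaluable subjects, and would exceed the scaled 1.145.

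The reply does not remove the layout problem. Separate maxima for six markers do not show whether they belong to the same subject, or what any subject's composite was. The shift tables do not cover this panel. A listing is not a summary, and adverse event reporting depends on the investigator's judgement of significance.

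**Conclusion.** The point holds as a reporting gap that is cheap to close. Two parts need no assumption: the Table 14.3.5.4.2 shell lacks the cohort columns that SAP 6.1.2 requires, and the threshold is stated only for n=20. The shell also shows no interval and no spread, and no visible table gives the composite per subject.

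The size of the dilution rests on the assumed composite formula and on unaffected subjects staying at 1.0. The n=30 figures also rest on 1/sqrt(n) scaling, and the 1.31 figure on 15/15 cohorts. Within those limits, rises such as 10-fold in 1 of 20 or 3-fold in 3 of 30 can leave the GM CM under the line. A GM CM below the threshold is therefore not, by itself, evidence of no tubular injury. Because of the redaction, further rules may exist that cannot be seen.

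**What to change.** In Table 14.3.5.4.2 and Figure 14.5:

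(a) show Cohort-1, Cohort-2 and Overall;

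(b) give a 95% CI for each GM CM, computed on the log scale and back-transformed;

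(c) replace the n=20 value with the user-guide threshold for the actual number of evaluable subjects in each group and at each visit;

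(d) add the median and maximum of the subject-level composite at each visit. Any individual cut-off should be labelled descriptive, since the visible documents give no source for one.

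Add one sentence to SAP 9.7 saying that a GM CM below the threshold is not by itself read as absence of tubular injury.

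The cost is a few rows and columns from data already collected, with no new samples. The drawbacks are wide intervals in small cohorts and some individual values that look high by chance and will need comment.
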